8.2.2.13 EQ-5D-5L score

EQ-5D-5L score will be described at the same timepoints as FBISI-18 score and will be analyzed using a MMRM. based on the windowing defined in section [11.1.1](#).

8.2.2.14 EQ VAS

EQ VAS will be described at the same timepoints as FBISI-18 score and will be analyzed using a MMRM based on the windowing defined in section [11.1.1](#)

8.2.2.15 Premedication

For this endpoint, descriptive statistics for the number of participants pre-medicated with acetaminophen and/or antihistamine will be presented at each injection/cycle.

Furthermore, the participant's global number of cycles with pre-medication will also be presented (with one global value per participant), with absolute value and relative value (number of cycles with pre-medication / number of cycles received by the participant * 100).

8.2.4 Further descriptive analyses

In addition to the analyses above-mentioned, the following descriptive analyses will be conducted to describe inclusions and follow-up visits:

-
- Number of participants included,
 - Number of participants excluded from the analyses and reason for exclusion,
 - Deviation to protocol,
 - Flow chart of participants' inclusions
 - Number of participants with progression/dead/alive at time of analysis.
 - Number of participants 'Lost to Follow-up'
 - Number of participants withdrawn from the study.

Early treatment discontinuation before progression together with reason for discontinuation will be described.

Finally, demography and baseline characteristics will be described in the Full Analysis Set and in the Safety Analysis Set, by histology group (Pure adenocarcinoma / Pure urothelial carcinoma / Urothelial carcinoma with variant / Other / Missing) and overall. Additional demography will be provided by patient's progression status (see section 5.3) and by type of subsequent treatment (ADC versus other, see section 5.3).

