## 7. RATIONALE AND BACKGROUND

Urothelial Cancer (UC) accounts for approximately 90% of all cancer of urinary tract (bladder, upper urinary tract, urethra). About 11 000 patients are newly diagnosed with an urinary tract cancer each year in France. Patients with metastatic UC have a dismal prognosis with a five-year survival rate of only 5%. Platinum-based polychemotherapy regimen is currently the first-line standard of care for patients with advanced/metastatic disease, but despite high initial response rates, durable and complete responses following first-line chemotherapy (ChT) are uncommon, and most patients will ultimately experience disease progression within nine months after initiation of treatment.

Avelumab (MSB0010718C, BAVENCIO®) is a human Immunoglobulin G1 monoclonal antibody directed against the programmed death ligand1 (PD-L1).

Avelumab in combination with Best Supportive Care (BSC) as a maintenance treatment had been evaluated versus BSC alone in a phase III randomized trial (JAVELIN Bladder 100) for locally advanced or metastatic Urothelial Carcinoma (adv/mUC) patients who have not progressed with first-line platinum-based chemotherapy. The JAVELIN Bladder 100 study has demonstrated a significant 7.1-months improvement in median Overall Survival with Avelumab+BSC as first-line maintenance versus BSC alone, with a 31% reduction of the death risk in the overall population (hazard ratio = 0.69 (95% CI, 0.56, 0.86), p<0.001). The results of the JAVELIN Bladder 100 had been presented at ASCO 2020 and published in the New England Journal of Medicine on September 18th, 2020.

On June 30th, 2020, U.S. Food and Drug Administration approved avelumab for maintenance treatment of patients with locally advanced or metastatic Urothelial Carcinoma who have not progressed with first-line platinum-containing chemotherapy.

On July 3rd, 2020 the French National Agency for Medicines and Health Products issued a cohort Temporary Authorization for Use (ATU) extension for avelumab in the first-line maintenance treatment of adult patients with locally advanced or metastatic Urothelial Carcinoma who have not progressed with first-line platinum-based chemotherapy and presenting an ECOG performance status of 0 or 1.

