3 INTERIM ANALYSES

A first interim analysis (IA1) will be performed for the population of participants who begun avelumab at least 6 months before the cut-off date of 31 January 2022 (Abstract for ESMO 2022 with associated publication) and then every year for publication purposes.

For the IA1, all efficacy and safety analyses will be presented for this population (8.2) and depending on the maturity of the data at least demographic/baseline characteristics data (8.2.4), time-to-event analyses and safety data (8.2.3) on the whole population (SAF population for safety analyses and FAS population otherwise). Subgroup analyses may be performed depending on the maturity of data and medical interest.

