5.3 SUBGROUPS

The primary and secondary objectives will be evaluated on the overall population and for prespecified subgroup.

- Main subgroup of interest: histology (UC with variant; UC without variant).
- Other subgroups of interest:
 - Histology (Pure UC; UC with variant, Pure adenocarcinoma, Other, Missing)
 - ECOG at avelumab initiation (PS 0-1; PS ≥ 2),
 - Locally advanced urothelial carcinoma versus metastatic urothelial carcinoma,
 - Previous ChT regimens (Cis/Gem, Carbo/Gem, Cis/Carbo/Gem, MVAC regimens, others),
 - Best response to 1st line chemotherapy (CR, PR, SD)
 - Regrouped best response to 1st line chemotherapy (CR+PR, SD),
 - Number of ChT cycles received in 1st line (< 4 cycles; ≥ 4 cycles and ≤ 6 ; > 6 cycles), Site of baseline metastases before ChT (visceral vs non-visceral),
 - Participants with an early relapse on avelumab and participants with a long-term response to avelumab. Patient is considered as early progressor if PFS is less than 3 months and if progression is observed. Patient is considered as long responder if PFS is equal or higher than 12 months, whatever the outcome.
This subgroup of interest will be used only for Overall Survival and progression free survival analyses, and baseline characteristics.
 - Delay between the end of ChT and the start of avelumab (< 4 weeks; between 4 and 10 weeks; > 10 weeks),
 - Delay between the end of ChT and the start of avelumab (< 4 weeks; ≥ 4 weeks),
 - ATU participants versus non ATU participants, site for the primary tumor (bladder, urethra, upper tract),
 - PD-L1 status,
 - FGFR abnormality,
 - Bajorin risk classification evaluated before ChT 1st line (0, 1, 2),
 - Presence of biological anomalies (neutropenia, lymphopenia, impaired renal function, anemia),
 - Use of concomitant treatments (corticosteroids/AIS/NSAIDs, sartans/ACE inhibitors, antibiotics, PPI) at avelumab initiation,
 - Type of subsequent treatment: Antibody-Drug Conjugate (ADC) treatment, chemotherapy, immunotherapy, targeted therapy, other. This classification will be made thanks to a medical review from Pfizer team.
 - Type of subsequent treatment: ADC versus Other.

PFIZER CONFIDENTIAL

CT24-WI-GL03-RF02 2.0 Non-Interventional Statistical Analysis Plan For Primary Data Collection Study

01-Jun-2020

Page 11 of 28

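### SAP 5.3 and 8.2.4: baseline tables by progression status set no common follow-up rule, so at IA1 and IA2 long responders can come only from the earlier part of the early-progressor start window

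*SAP*

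**What the plan says.** SAP 5.3 defines the two groups. For the first, "Patient is considered as early progressor if PFS is less than 3 months and if progression is observed". For the second, "Patient is considered as long responder if PFS is equal or higher than 12 months, whatever the outcome". It then limits their use: "This subgroup of interest will be used only for Overall Survival and progression free survival analyses, and baseline characteristics".

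SAP 8.2.4 plans the table, as additional demography by "progression status (see section 5.3) and by type of subsequent treatment (ADC versus other, see section 5.3"). The baseline row of the summary in SAP 8.2.5 lists progression status as a subgroup. Neither place sets a minimum time since first injection.

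SAP 3 defines the IA1 population as "participants who begun avelumab at least 6 months before the cut-off date of 31 January 2022", for an abstract and associated publication, with yearly analyses to follow. Depending on maturity, at least the baseline data of 8.2.4 are also to be shown for the whole population. On subgroups it says: "Subgroup analyses may be performed depending on the maturity of data and medical interest".

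Protocol 7 gives the access history. The ATU of 3 July 2020 covered patients "presenting an ECOG performance status of 0 or 1". The indication authorised on 21 January 2021 is described without an ECOG limit.

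**The concern.** A patient who started avelumab four months before the cut-off can already be an early progressor but cannot yet be a long responder. At any analysis where some participants have less than 12 months since first injection, the two columns of the table are therefore drawn from different spans of calendar time. Any characteristic that changed over that time will differ between the columns, even if it has no bearing on outcome.

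Access changed during that time: ECOG was capped at 0-1 under the ATU, and the authorised indication is quoted without that cap. ECOG at avelumab initiation is one of the listed baseline characteristics. A reader of a published interim table could take ATU access or good ECOG as a mark of long response when part or all of the difference comes from start date. This is separate from any immortal-time problem in OS or PFS curves by the same grouping, because it distorts the baseline table itself.

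**Working it through.** The plan gives no figure for this table. Its only planning figure, the confidence interval for median OS in Protocol 9.5, reproduces: with m = 29 × ln 2 = 20.1 months, 2nm/χ² on 2n degrees of freedom gives 18.59 to 21.81 for n = 600, against the stated 18.6 to 21.8. It has no bearing on this point.

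**Inputs from the documents**
- ATU opening 3 July 2020, ECOG 0-1; authorisation 21 January 2021 (Protocol 7).
- IA1 cut-off 31 January 2022, population started by 31 July 2021 (SAP 3).
- IA2 in Q4 2022, IA3 in Q4 2023, IA4 and last visit in Q4 2024 (Protocol 6). With 2 years of follow-up for the last patient (Protocol 9.1), inclusion ends about Q4 2022.

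**Assumptions, not in the documents**
- Uniform starts from 3 July 2020, at latest to 31 December 2022.
- 21 January 2021 as a proxy for the end of ECOG-restricted access.
- PFS unrelated to access period or ECOG; exponential PFS with a median of 3, 5 or 8 months (the choice hardly matters).
- ECOG ≥2 in 0% of starters before authorisation and 5%, 10% or 20% after.
- IA2 cut-off between 1 October 2022 and 31 January 2023; IA3 cut-off between 1 October and 31 December 2023.

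**IA1 windows (days counted inclusively)**
- 3 July 2020 to 21 January 2021: 203 days.
- Long responders must have started by 31 January 2021: 213 days, of which 213 − 203 = 10 follow authorisation; 10/213 = 4.7%.
- Early progressors in the IA1 population may have started up to 31 July 2021: 394 days, of which 394 − 203 = 191 follow authorisation; 191/394 = 48%.
- In the whole population to the cut-off, about 62% of early progressors would be post-authorisation starters, allowing for the shorter follow-up of the latest ones.
- If the start rate doubled after authorisation, the IA1 shares become 20/(203 + 20) = 9% and 382/(203 + 382) = 65%.

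**ECOG ≥2 at IA1 with no true link to PFS** (assumed share × post-authorisation share)

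| ECOG ≥2 among post-authorisation starters | Early progressors | Long responders |
|---|---|---|
| 5% | 2.4% | 0.2% |
| 10% | 4.8% | 0.5% |
| 20% | 9.7% | 0.9% |

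**Later analyses (post-authorisation share)**

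| Analysis | Early progressors | Long responders |
|---|---|---|
| IA2 | 74-77% | 55-65% |
| IA3 | 75-78% | 75-78% (gap at most 2.4 points) |
| IA4, final | no gap | no gap |

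For example, an IA2 cut-off of 1 October 2022 gives a long-responder window of 456 days, (456 − 203)/456 = 55%, against 74% for early progressors. At 10% ECOG ≥2, IA2 would show about 7.4-7.7% versus 5.5-6.5%.

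**With both groups limited to starts at least 12 months before cut-off**, the IA1 groups share one 213-day window, 4.7% of it after authorisation. The artefactual ECOG gap is then zero under these assumptions.

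**The case against.** Several points on the other side are sound.

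- **Timing.** The SAP is version 1, dated 2 December 2022, after the IA1 cut-off and after IA1's planned quarter (Q2 2022). A change cannot be expected to alter an IA1 table already produced, and the effect is largest there. This stands: the change reaches IA2 onward and any further use of the IA1 table.
- **Discretion.** Subgroup analyses at IA1 are optional and depend on maturity, so the table could be withheld. That is true, but maturity is not defined and does not align the groups. The same section also puts the baseline data of 8.2.4 in the minimum set for the whole population, subject to maturity.
- **Descriptive only.** SAP 4 states no hypotheses and purely descriptive analyses. This limits the severity, but a descriptive table in a publication can still mislead.

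A reader might infer more than the documents support:

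- *That the two groups come from different access periods.* They do not. The long-responder window is nested in the early-progressor window, and about 52% of the latter at IA1 (203/394) is also before or on the authorisation date.
- *That ECOG differs by design, by about ten-fold.* What follows is that ECOG ≥2 is nearly excluded from IA1 long responders, if the authorisation date marks the end of restricted access. The documents give neither the ECOG ≥2 share nor the ATU end date, and ATU starts after 21 January 2021 would shrink the contrast. A ten-fold ratio rests on a near-zero denominator; at an assumed 10% the absolute gap is about 4 points. If data ran to 30 April 2022, the long-responder window would be 302 days with 99 after authorisation (33%), and the gap at 10% would be 4.8% versus 3.3%.
- *That all the published interims are affected.* Only IA1 and IA2 are affected to any material degree.

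**Conclusion.** The point holds as a minor one. The definitions in SAP 5.3 require unequal follow-up, and no rule in 5.3, 8.2.4 or 8.2.5 gives both groups the same opportunity to be classified. That follows from the text and needs no assumption. The calendar imbalance at IA1 (about 5% versus 48% post-authorisation) rests on uniform starts and remains if starts doubled after authorisation. The ECOG figures are illustrations over an assumed range of 5-20% and should not be read as estimates. The imbalance shrinks at IA2, is at most 2.4 points at IA3, and disappears at IA4 and the final analysis provided inclusion ends about Q4 2022 as planned. The primary endpoint is not affected.

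**What to change.** In SAP 5.3 and 8.2.4, state that at any analysis the tables by progression status include only participants whose first injection was at least 12 months before the data cut-off, and that the number left out is reported. Apply this from IA2 onward and to any further use of the IA1 table.

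The cost is one sentence and a filter on first-injection date, plus fewer early progressors in interim tables: about 46% fewer at IA1 under uniform starts (1 − 213/394). At IA2 between 37% and 45% of starters would be left out, depending on the cut-off. At the final analysis nobody is lost, because the last patient is followed for 2 years.

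Showing the table by ATU status, already a subgroup in SAP 5.3, is an alternative that drops no patients. It exposes the access-period effect but does not give the two groups equal opportunity to be classified.

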8.2.5 Summary of analyses

Outcome	Analysis Set	Supports Protocol Objective Number	Subgroups	Statistical Method	Covariates/ Strata	Missing Data
OS	FAS	1	NA	Kaplan-Meier	NA	Excluded
OS	FAS	1	See section 5.3	Kaplan-Meier	NA	Excluded
OS 2	FAS	2	NA	Kaplan-Meier	NA	Excluded
PFS	FAS	2	NA	Kaplan-Meier	NA	Excluded
PFS 2	FAS	2	NA	Kaplan-Meier	NA	Excluded
ORR	FAS	2	NA	Descriptive statistics	NA	Excluded
DOR	FAS	2	NA	Kaplan-Meier	NA	Excluded
DOT	FAS	2	NA	Kaplan-Meier	NA	Excluded
Progression description	FAS	2	NA	Descriptive statistics	NA	Excluded
OS subsequent	FAS	2	NA	Kaplan-Meier	NA	Excluded
PFS subsequent	FAS	2	NA	Kaplan-Meier	NA	Excluded
ORR subsequent	FAS	2	NA	Descriptive statistics	NA	Excluded
DOT subsequent	FAS	2	NA	Kaplan-Meier	NA	Excluded
FBISI-18 score	FAS	2	NA	Descriptive statistics + MMRM	NA	Excluded
EQ-5D-5L score	FAS	2	NA	Descriptive statistics + MMRM	NA	Excluded
EQ-VAS score	FAS	2	NA	Descriptive statistics + MMRM	NA	Excluded
Premedication	FAS	2	NA	Descriptive statistics	NA	Excluded
Safety analyses	SAF	2	Histological group Subsequent treatment category	Descriptive statistics	NA	Excluded
Baseline characteristics	FAS & SAF	2	Progression status Subsequent treatment category	Descriptive statistics	NA	Excluded

PFIZER CONFIDENTIAL

CT24-WI-GL03-RF02 2.0 Non-Interventional Statistical Analysis Plan For Primary Data Collection Study 01-Jun-2020

Page 25 of 28

090177e19bffc15d\Approved\Approved On: 02-Dec-2022 20:57 (GMT)

9 LIST OF TABLES AND TABLE SHELLS

Please refer to the Excel file CT24-WI-GL14-RF04 2.0 Non-Interventional Study List of Tables 01-Jul-2019.xlsx

11 APPENDICES

11.1 APPENDIX 1: DATA DERIVATION DETAILS

11.1.1 Definition and use of visit windows in reporting

Data will be summarized in tables by visit (timepoint) when applicable. The following visit label and visit windows will be applied for all PRO endpoints:

Visit Label	Target Day	Visit Window
Baseline	1	Day 1 or before
Week 6	42	Day 2 to Day 66
Month 3	91	Day 67 to Day 137
Month 6	183	Day 138 to Day 228
Month 9	274	Day 229 to Day 320
Month 12	365	Day 321 to Day 410
Month 15	456	Day 411 to Day 501
Month 18	548	Day 502 to Day 593
Month 21	639	Day 594 to Day 684
Month 24	730	Day 685 to Day 775

In case of multiple observations falling within a given window, the observations selected for analysis will be identified as follows:

1. The observation closest to the target day will be used.
2. If the observations are at equal distance from the target day in absolute value, the one with a correct nominal visit label will be used.

PFIZER CONFIDENTIAL

CT24-WI-GL03-RF02 2.0 Non-Interventional Statistical Analysis Plan For Primary Data Collection Study

01-Jun-2020

Page 26 of 28

3. If neither (1) nor (2) can be used to identify the observation windowing, then the latest observation within the analysis window will be used.

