### 9.1.2. Secondary endpoints

- OS from the start of the chemotherapy used in 1st line: time between the first injection of the chemotherapy used in 1st line and the date of death from any cause.
- PFS1: time between the first injection of avelumab and the date of progression or death from any cause. Progression status will be defined according to RECIST 1.1.
- PFS2: time between the first injection of avelumab and the date of progression or death from any cause during the 2nd line of treatment post-avelumab. Progression status will be defined according to RECIST 1.1.
- ORR: proportion of patients with a Complete Response or Partial Response as a best response during the avelumab treatment. Responses to treatment will be defined according to RECIST 1.1.
- DOR: time between the beginning of the response and progression or death from any cause.
- DOT: time between the first and last dose of avelumab.
- Patterns of progression under avelumab: metastatic sites and type of progression (new lesion(s)/progression of known lesion(s)).
- Subsequent treatments and response to these treatments: DOT, PFS, ORR and OS.
- Safety: AEs of any type, grade 3-4 AEs, AEs leading to interruption or discontinuation, AEs leading to death.

090177e1a41aac13\Final\Final On: 28-Jul-2025 13:50 (GMT)

- Premedications (acetaminophen and antihistamine): Proportion of patients who received a premedication at each injection of avelumab. Median number of cycles with premedication. To evaluate the correlation between infusion-related reactions and premedication.
- Evolution of PROs NCCN/FACT FBISI-18 and EQ-5D-5L scores during avelumab treatment.

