8.2.2.12 FBISI-18 score

Scores will be described at the following timepoint:

- Avelumab initiation (baseline)
- After initiation if the participant is still treated with avelumab:
 - o 6 weeks,
 - o 3 months,
 - o Every three months for up to 2 years,
 - o Tumor progression if so,
- Avelumab discontinuation (whatever the reason is).

The FBISI-18 score will be analyzed using a MMRM based on the windowing defined in section [11.1.1](#).

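### In the PRO mixed models, day-only windows can let a discontinuation questionnaire count as, or displace, a scheduled on-treatment visit; separately, Week 6 opens on Day 2

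*SAP*

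**What the plan says.** Protocol 9.1 and Table 2 in Protocol 9.3 ask patients who start avelumab after study start for PRO forms on these occasions: at initiation; at 6 weeks, 3 months and then three-monthly up to 2 years, and at tumour progression, in each case only while avelumab continues; and at discontinuation. The secondary endpoint in Protocol 9.1.2 is "Evolution of PROs NCCN/FACT FBISI-18 and EQ-5D-5L scores during avelumab treatment".

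SAP 8.2.2.12 repeats this list for describing the FBISI-18. The scheduled and progression timepoints sit under the condition that treatment continues, and a separate entry reads "Avelumab discontinuation (whatever the reason is". SAP 8.2.2.13 and 8.2.2.14 adopt the same timepoints for EQ-5D-5L and EQ VAS. All three sections base the mixed model for repeated measures (MMRM) on the windows in SAP 11.1.1. SAP 8.1.4 fits visit as a categorical factor with baseline as one level, under a missing-at-random (MAR) assumption.

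SAP 11.1.1 states: "The following visit label and visit windows will be applied for all PRO endpoints". Baseline is "Day 1 or before". Nine windows follow, from Week 6 (target Day 42, Day 2 to 66) to Month 24 (target Day 730, "Day 685 to Day 775"). If several forms fall in one window, three rules apply in order:

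1. "The observation closest to the target day will be used".
2. At equal distance, "the one with a correct nominal visit label will be used".
3. Failing both, "then the latest observation within the analysis window will be used".

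The table has no row for progression or discontinuation forms, and no rule sets them aside.

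**The concern.** Window assignment depends on the day alone, so a form completed because the patient stopped avelumab receives a scheduled label like any other. The MMRM estimates at the scheduled visits are meant to describe scores during treatment. They can instead mix on-treatment scores with scores taken at stopping, in a proportion set by the day on which each patient happens to stop. Rule 1 can also discard a genuine scheduled form in favour of the discontinuation form.

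A progression form is different. The documents collect it while avelumab continues, so it fits the endpoint. The only problem there is that it can displace a scheduled form.

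A second, smaller matter sits at the start of the table. Week 6 begins the day after baseline closes, so a form completed shortly after the first injection, or an initiation form completed late, falls into Week 6.

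**Working it through.** **Coverage.** The nine post-baseline windows are Day 2–66, 67–137, 138–228, 229–320, 321–410, 411–501, 502–593, 594–684 and 685–775. Each starts the day after the last one ends, so they cover 775 − 2 + 1 = 774 of 774 days. Every form dated Day 2–775 gets a scheduled label; later forms get none.

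**Boundaries.** Midpoints between successive targets from Day 42 on are 66.5, 137, 228.5, 319.5, 410.5, 502, 593.5 and 684.5. The boundaries follow them to within a day. Day 320 is the exception: it lies in Month 9, 46 days from Day 274, but only 45 days from Day 365. The midpoint of Day 1 and Day 42 is 21.5, yet Week 6 opens on Day 2, which adds 20 days (Day 2–21).

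**A discontinuation form standing as a scheduled visit.** A patient stops on Day 150. Day 150 lies in Day 138–228, so the form is Month 6. The patient was off avelumab before target Day 183, so no Month 6 on-treatment form is due.

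**A discontinuation form displacing a scheduled form.** A scheduled Month 3 form is dated Day 80 and a discontinuation form Day 100. Both lie in Day 67–137. Distances from Day 91 are 11 and 9 days, so rule 1 keeps the discontinuation form. There is no tie, so the nominal label is never consulted.

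**Illustrative share of visit values.** The documents give no time-on-treatment distribution and no completion rates. Assume exponential time on avelumab with median m = 5 to 8 months, and stoppers completing forms as often as continuers. Then S(d) = 0.5^(d / (30.44 m)). Patients who stop inside a window but before its target supply the share

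(S(lower) − S(target)) / S(lower) = 1 − 0.5^((target − lower) / (30.44 m)).

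| Visit | target − lower | m = 5 | m = 6 | m = 8 |
|---|---|---|---|---|
| Month 3 | 91 − 67 = 24 | 0.104 | 0.087 | 0.066 |
| Month 6 | 183 − 138 = 45 | 0.185 | 0.157 | 0.120 |
| Month 9 | 274 − 229 = 45 | 0.185 | 0.157 | 0.120 |
| Month 12 | 365 − 321 = 44 | 0.182 | 0.154 | 0.118 |

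This gives about 7–19%, before counting displaced scheduled forms. If stoppers complete forms half as often, a share p becomes 0.5p / (0.5p + 1 − p). For Month 6 to 12, 0.118 becomes 0.059 / 0.941 = 0.063 and 0.185 becomes 0.0925 / 0.9075 = 0.102, so about 6–10%.

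**Early forms and Week 6.** A form on Day 2–21 is 40 to 21 days from Day 42. Any form on Day 22–62 is at most 20 days away and wins. A form on Day 63–66 is 21 to 24 days away, so a form on Day 2–17 (25 to 40 days) loses to that as well. A form on Day 18–21 can tie with or beat only a form on Day 63–66. The early form is therefore the Week 6 value essentially when no nearer form exists, and is otherwise dropped. Either way it is not a baseline value.

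**The case against.** Several counter-arguments have force.

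- **Separate timepoints exist.** SAP 8.2.2.12 keeps progression and discontinuation as their own descriptive timepoints. A reader might infer that every PRO table relabels these forms, but the documents do not support that. The relabelling is explicit for the MMRM. For the descriptive tables, 8.2.2.12 and 11.1.1 conflict and need reconciling.
- **The label is not ignored.** Rule 2 uses it, though only for exact ties, which protects neither worked example.
- **Progression forms are on-treatment.** A reader might class them with discontinuation forms as scores taken off treatment. Protocol 9.1 and SAP 8.2.2.12 place them under continuing treatment.
- **Discontinuation scores carry information.** Under MAR, the last score before dropout helps the model represent those who leave, and it can be seen as the end point of the on-treatment course. This stands: it is a reason to report an all-forms model, and against dropping these scores altogether. But the SAP does not state that choice, and it gives no reason for a discontinuation form to replace a scheduled one.
- **The Week 6 point is limited.** A post-dose form is reasonably not called baseline, and it usually loses to a true Week 6 form. Because baseline is a level of the visit factor, a patient without one can still contribute to the MMRM, although an individual change from baseline (SAP 6.1.1) cannot be computed.

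**Conclusion.** The point holds for the three PRO mixed models. As written, a discontinuation form can be analysed as a scheduled visit or displace a scheduled on-treatment form, which does not match SAP 8.2.2.12 or the endpoint in Protocol 9.1.2. No other section repairs this. The mechanism follows from the literal text and needs no assumption.

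The size is unknown. It would be wrong to read 7–19% as an estimate for this study: it rests on exponential time on avelumab, a median of 5–8 months and equal form completion, none of which the documents give. The 20 extra days in Week 6 are calendar days, not a count of affected forms.

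The consequence is confined to secondary, descriptive PRO endpoints in patients who started avelumab after study start. OS is not affected.

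**What to change.** Amend SAP 11.1.1, and align 8.2.2.12 to 8.2.2.14 with it:

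1. Within a window, a scheduled form completed on avelumab takes priority over a progression or discontinuation form, whatever their distances from the target. The three existing selection rules then apply among scheduled forms.
2. Discontinuation forms are summarised under their own timepoint and do not enter the scheduled on-treatment means. Report the MMRM also with all forms windowed as now, because under MAR the last score before dropout is informative. State that the descriptive tables follow the same classification.
3. Open the Week 6 window at Day 22 and list forms from Day 2–21 only. This protects Week 6 but does not restore a missing baseline.

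The cost is SAP wording, one programming rule, somewhat fewer values per scheduled visit and one extra model run per score. It assumes that the database identifies the type of each form. The SAP mentions only a nominal visit label, so this should be confirmed. No new data collection is needed if it does.
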